### 9.3 Subgroups and exploratory analyses

#### 9.3.1 Subgroup analyses

The following subgroup analyses have been planned *a priori*:

1. Primary outcome (malaria incidence) will be stratified according to the following 3 age strata: < 15 years, 5-15 years, and over 15 years.
2. Secondary outcomes for LLIN ownership, coverage and use will be stratified according to the following 3 age strata: < 15 years, 5-15 years, and over 15 years.

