13.5 Analytical plan

All analyses will be conducted using an intention-to-treat approach. For our primary outcome, we will compare cluster level estimates of the incidence of malaria between intervention and control arms using a mixed effects Poisson regression model since randomization will occur at the district level (each district will include two clusters, randomized to the two study arms). We will also adjust our model for baseline estimates of malaria incidence (3 months prior to the intervention) and additional cluster-level covariates from the cross-sectional surveys including treatment seeking behaviour (to account for cases of malaria not captured at the MRCs) and the diagnostic accuracy of RDTs vs microscopy (to account for differences in the use of these diagnostic tests between clusters). The effect of the intervention will be expressed as an incidence rate ratio (incidence in the intervention arm/incidence in the control arm). Our primary analysis will evaluate malaria incidence over 24-months following the intervention. We will also perform secondary analyses of malaria incidence stratified by time following the intervention (year 1 vs year 2).

For our secondary outcomes, comparisons between intervention and control arms will be made using an individual-level approach to the analysis due to the large number of clusters per arm. Prevalence measures (parasitaemia, anaemia, LLIN ownership, LLIN coverage, LLIN access and LLIN use) will be compared using mixed effects logistic regression models with random effects at the level of the cluster and household. The effect of the intervention will be expressed as the prevalence ratio (prevalence in the intervention arm/prevalence in the control arm). For comparison of vector density, LLIN integrity, and bio-efficacy (funding permitting) between treatment arms, regression models will be used with generalized estimating equations to allow for within-cluster correlations. The effect of the intervention will be expressed as the density or rate ratio (density or rate in the intervention arm / density or rate in the control arm). Chemical analysis of withdrawn LLINs and their unused controls will be compared using the Wilcoxon rank sum test.

14 Ethical considerations

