## 8.2 Secondary outcomes from cross-sectional surveys

Secondary outcomes from the 12 and 24 month cross-sectional surveys will include the following:

1. Prevalence of parasitemia in children 2-10 years of age - defined as the proportion of children with a positive thick blood smear by microscopy.
2. Prevalence of anemia in children 2-4 years of age - defined as the proportion of children with a hemoglobin level < 11 g/dL.
3. Measures of LLIN ownership, coverage and use defined as follows:
  - a. LLIN ownership - the proportion of households that owned at least one LLIN),
  - b. Adequate LLIN coverage - the proportion of households that owned at least one LLIN for every two residents.
  - c. LLIN access - proportion of residents who could sleep under a LLIN, if each LLIN in the household were used by up to two residents
  - d. LLIN use - the proportion of household residents who reported sleeping under an LLIN the previous night.

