### 8.2.1 Analytical approach

All analyses will be conducted using an intention-to-treat approach according to the treatment allocations the clusters were randomized to. Separate analyses will be conducted for the 12 and 24 month cross-sectional surveys. We will compare individual level estimates of the prevalence of parasitemia and anemia between the intervention (PPF LLINs) and control arm (PBO LLINs) using a mixed effects logistic regression model with random effects at the level of the cluster and household. We will compare household level estimates of LLIN ownership, coverage, and use using a mixed effects logistic regression model with a random effect at the level of the cluster. Effects of the intervention will be expressed as odds ratios (odds in the intervention arm/odds in the control arm).

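### The a priori age strata in SAP 9.3.1 overlap (<15, 5-15, over 15); separately, for LLIN use, which is to be split by age, the SAP and the protocol specify different analyses

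*SAP*

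**What the plan says.** SAP 9.3.1 lists two subgroup analyses planned a priori. The first reads "Primary outcome (malaria incidence) will be stratified according to the following 3 age strata: < 15 years, 5-15 years, and over 15 years". The second begins "Secondary outcomes for LLIN ownership, coverage and use will be stratified according to the following 3 age strata" and prints the same cut-points. No other section of either document gives age cut-points for these analyses, and SAP 9.3.2 plans no exploratory analyses.

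SAP 8.2 introduces the net outcomes as a group: "Measures of LLIN ownership, coverage and use defined as follows". Ownership and adequate coverage are counted in households; adequate coverage, for example, is "the proportion of households that owned at least one LLIN for every two residents". Use is counted in people: "the proportion of household residents who reported sleeping under an LLIN the previous night". Access is also expressed as a proportion of residents, but is worked out from the number of nets in the household.

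The two documents analyse these outcomes differently:

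- SAP 8.2.1: "We will compare household level estimates of LLIN ownership, coverage, and use using a mixed effects logistic regression model", with a random effect for cluster only. Results are reported as odds ratios.
- Protocol 13.5: for the secondary outcomes, "comparisons between intervention and control arms will be made using an individual-level approach to the analysis". The prevalence measures, with LLIN ownership, coverage, access and use all listed, "will be compared using mixed effects logistic regression models with random effects at the level of the cluster and household". Results are reported as prevalence ratios.

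**The concern.** Subgroups are normally read as distinct groups of people. Under the printed cut-points, the first two incidence results would share every case and all person-time from ages 5 to 14. They could not be compared as separate age groups, and the three strata would not add up to the total. No under-5 result would be produced, and adding one later would depart from the plan, because these are the only subgroup analyses declared.

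The LLIN-use problem is separate but meets the first at item 2 of SAP 9.3.1. That item asks for use by age. Age belongs to a resident, whereas SAP 8.2.1 works with household estimates. Protocol 13.5 works with individuals but differs from the SAP in its random effects and in the effect measure. An analyst therefore has two incompatible instructions for use at 12 and at 24 months, and the SAP's version does not support the age split that the SAP itself requires. In an open-label trial, it is better that neither choice is left until results are visible.

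**Working it through.** **1. Age strata.** The inputs are the cut-points in SAP 9.3.1, read in completed years.

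- <15 covers ages 0-14: 15 ages.
- 5-15 covers ages 5-15: 11 ages.
- Together they cover ages 0-15: 16 ages.
- Ages counted twice: 15 + 11 - 16 = 10, namely ages 5 to 14. As a share of the ages covered, 10/16 = 62.5%.

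| Completed age | Stratum or strata as printed |
|---|---|
| 0-4 | <15 only, pooled with 5-14 |
| 5-14 | <15 and 5-15 |
| 15 | 5-15 only |
| 16 and above | over 15 only |

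No age is left out. If ages are read as exact rather than completed, the overlap is still ten years.

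If the first cut-point were <5, the first two strata would hold 5 + 11 = 16 ages, equal to the 16 they cover. The overlap would be 0 and every age would fall in exactly one stratum.

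**2. LLIN use, the two plans side by side.**

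| Item | SAP 8.2.1 | Protocol 13.5 |
|---|---|---|
| Unit | household | individual |
| Random effects | cluster | cluster and household |
| Effect measure | odds ratio | prevalence ratio |
| Model family | mixed effects logistic | mixed effects logistic |

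Three of the four items differ.

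**3. The four net measures against those plans.**

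| Measure (SAP 8.2) | Counted in | Named in SAP 8.2.1 | Can it be split by resident's age? |
|---|---|---|---|
| Ownership | households | yes | no, a household has no single age |
| Adequate coverage | households | yes | no, same reason |
| Access | residents, derived from household nets | no | only with a rule assigning access to persons |
| Use | residents | yes | yes, from resident-level records |

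A household with a young child, a schoolchild and an adult spans several strata at once. One household figure for use cannot be placed in any of them. Nor does SAP 8.2.1 say how such a figure would enter a logistic model: as a count of residents, a share, or a yes/no outcome.

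Conversely, ownership and adequate coverage give one record per household per survey. A household random effect, as in protocol 13.5, cannot be estimated separately for them.

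So the household-level plan suits ownership and adequate coverage, the individual-level plan suits use, and neither document settles access.

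**The case against.** The strongest reply is that the strata are a misprint. One digit changes <15 to <5, the text promises three strata, and the second begins at 5. Elsewhere the documents treat under-5s as a group: haemoglobin is measured in children below that age (SAP 5.3.7), and the cited stepped-wedge trial of pyriproxyfen nets enrolled ages 6-59 months (SAP 1.1). An analyst would probably read it that way. This makes the intention evident, but the error is printed twice in an operative analysis rule and nothing corrects it, so confirmation is still needed.

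On LLIN use, the SAP's household-level approach may be a deliberate change. The documents state no order of precedence, so the protocol's model does not win by default. What stands is that splitting use by age needs person-level or age-specific records, which a single household estimate does not provide.

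Some stronger readings are tempting, but the documents do not support them:

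- A reader might infer that SAP 8.2.1 wrongly omits a household random effect. With one record per household the omission follows from the chosen unit; it matters only if use is modelled by resident.
- A reader might infer that the protocol 13.5 model fits access as written. Access is derived from nets per household, and neither document says how it is assigned to individuals.
- A reader might infer that ownership and coverage are definitely to be split by residents' age. The phrase in item 2 may only repeat the group heading in SAP 8.2.
- A reader might infer that age-specific incidence has no denominator. The SAP names no source for age-specific populations, but a census of the target areas is planned. This is missing detail, not a contradiction.

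**Conclusion.** Both parts hold. The age strata in SAP 9.3.1 are not mutually exclusive: ten single years of age are in two strata, and none of the three strata isolates under-5s. For LLIN use, the SAP and the protocol conflict on unit, random effects and effect measure, and the SAP's household-level estimate cannot deliver the age split in its own subgroup plan.

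The reach is limited. The primary analysis pools all ages and is untouched; the effect is confined to the age subgroup analyses and to LLIN use as a secondary outcome. The conflict over effect measure is somewhat wider, because in both documents it also covers parasitaemia and anaemia. The ten years and the 62.5% are counts of ages, not shares of cases or residents, and they say nothing about the size or direction of bias in any estimate. That <5 was meant is an inference from the structure of the list; the documents do not confirm it.

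This should be corrected before analysis, but it does not threaten the trial's main conclusion.

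**What to change.** In a SAP amendment dated before analysis:

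1. Replace both lists in 9.3.1 with mutually exclusive, exhaustive strata in completed years. The study team should confirm that <5, 5-15 and over 15 is what was meant.
2. In 8.2.1, model LLIN use at resident level with random effects for cluster and household, and apply the age strata in item 2 of 9.3.1 to that measure.
3. Keep one record per household with a cluster random effect for ownership and adequate coverage, and state that these are not stratified by age.
4. Name access in 8.2.1. Stratify it by age only if a rule assigning access to individual residents is stated.
5. Choose the odds ratio or the prevalence ratio and state it in both SAP 8.2.1 and protocol 13.5. If it is the prevalence ratio, say how it is obtained from a logistic model.

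The cost is a few lines in SAP 9.3.1 and 8.2.1 and a matching edit to protocol 13.5. No new data are needed if the household questionnaire records each resident's age. That is an assumption: SAP 5.3.5 says only that children for the clinical survey are identified from the questionnaire.

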#### 9.3.2 Exploratory analysis

No exploratory analyses are planned.

### 9.4 Missing data

For estimates of malaria incidence, adjustments will be made when calculating the number of cases of laboratory-confirmed malaria by adding estimates for the following categories of patients: 1) Malaria cases due to missing data on diagnostic testing = patients residing in the target area with suspected malaria but no laboratory test done multiplied by the test positivity rate among patients residing in the target area with suspected malaria and tested for malaria. 2) Malaria case due to missing data on location of residence = patients with laboratory confirmed malaria with missing data on village of residence multiplied by the proportion of patients with laboratory confirmed malaria who reside in the target area.

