Figure 7. Estimating malaria incidence at the Anyeke MRC.

Anyekie MRC test positivity rate and malaria incidence by month from April 2019 to March 2020, with incidence estimates calculated using four different sources) to estimate the population of the target area.

cases of suspected malaria with no test results, plus the estimated number of cases of laboratory confirmed malaria cases with missing information on village of residence. For the denominator, four population databases have been consulted, including High Resolution Settlement Layer (HDSL), Uganda Bureau of Statistics (UBOS), the AfriPop project (AFRIPOP), and Oak Ridge National Laboratory's LandScan (LANDSCAN) (Figure 7). In the future, we plan to conduct a census survey of each MRC target area to confirm the population. By establishing the capacity to estimate malaria incidence for the target areas of the MRCs, we have built a platform which will allow us to assess the impact of LLINs distributed through the national LLIN campaign on malaria incidence on a wide scale.

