13.3 Measuring the incidence of malaria in the MRC target areas

Incidence of malaria for each MRC target area will be calculated by dividing the number of laboratory confirmed cases of malaria from patients who report living within the target area, per unit time over the 24-month follow-up period, by the total population of target area, with two correction factors: 1) for patients who reside within the target area with suspected malaria who do not undergo laboratory testing, and 2) for patients with laboratory confirmed malaria whose village of residence is missing.

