### 8.1 Primary outcome

The primary outcome of the study will be the cumulative incidence of malaria over the 24 month follow-up period. The total number of cases of malaria for each MRC target area will be the number of laboratory confirmed cases of malaria from patients who report residing in the target area over the 24 month follow-up period, with two correction factors: 1) for patients who reside within the target area with suspected malaria who do not undergo laboratory testing, and 2) for patients with laboratory confirmed malaria whose village of residence is missing. The population of the MRC target area will be used for incidence calculations.

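### Under SAP 9.4, suspected malaria patients with neither a test nor a recorded village enter neither correction, so the primary case count is slightly low; the residence share also lacks a stated denominator

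*SAP*

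**What the plan says.** The primary outcome counts laboratory-confirmed cases among patients who report living in the target area of the Malaria Reference Centre (MRC). SAP 9.4 then adds two estimates.

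- Correction 1 counts "patients residing in the target area with suspected malaria but no laboratory test done". Its multiplier is the positivity observed in suspected patients from the same area who did have a test.
- Correction 2 starts from confirmed cases for whom no village was entered. That number is "multiplied by the proportion of patients with laboratory confirmed malaria who reside in the target area".

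The other descriptions name the same two groups. SAP 8.1 gives the first correction as one "for patients who reside within the target area with suspected malaria who do not undergo laboratory testing". Protocol 13.3 gives the second as one "for patients with laboratory confirmed malaria whose village of residence is missing". Protocol 1.5 describes the numerator in looser terms, as confirmed cases plus an estimate for untested suspected cases, "plus the estimated number of cases of laboratory confirmed malaria cases with missing information on village of residence". It gives no formula and no further term. Neither document states how often a test or a village is missing.

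**The concern.** Each correction handles one missing field and needs the other to be present. Correction 1 requires residence in the target area to be known. Correction 2 requires a positive test. A suspected patient with no test and no village fails both conditions, although some of these patients are target-area malaria cases.

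There is a second, softer problem. Correction 1 states the denominator of its multiplier: tested target-area residents. Correction 2 does not say whether its share is taken over all confirmed cases or only those whose village was recorded. Two analysts following the text could compute different values of the primary outcome.

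At stake are the absolute incidence in each cluster and whatever is built on it, such as cases averted. The between-arm comparison would be affected if register completeness differed by arm.

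**Working it through.** The documents give no corrected count or missing rate, so there is no figure of the plan's to reproduce. The formulas can be checked algebraically.

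**Inputs.** The two terms are those of SAP 9.4. S is the number of suspected patients seen at the MRC, q the true target-area share and p the test positivity. The share untested is u and the share without a recorded village is m. I assume that u and m are independent, that both fields are missing at random, and that p is the same inside and outside the target area. The range of 2% to 20% for u and m is an assumption.

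**Target.** Cases among target-area patients presenting to the MRC = S·q·p.

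**What is counted**

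- Confirmed, village recorded in the target area: S(1−u)(1−m)qp
- Correction 1: S·u(1−m)qp
- Correction 2: S(1−u)m·p × share
- Untested with no village: nothing, although S·u·m·q·p cases are expected there

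**Share over confirmed cases with a recorded village.** The share equals q, so counted/target = (1−m) + (1−u)m = 1 − um. The undercount is um.

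**Share over all confirmed cases.** The share equals (1−m)q, so counted/target = (1−m) + (1−u)m(1−m) = 1 − m² − um(1−m). The undercount is m² + um(1−m).

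| u / m | Recorded-village share | All-confirmed share |
|---|---|---|
| 2% / 2% | 0.04% | 0.08% |
| 5% / 5% | 0.25% | 0.49% |
| 10% / 10% | 1.0% | 1.9% |
| 20% / 20% | 4.0% | 7.2% |

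**Worked example.** Take S = 10,000, q = 0.3, p = 0.5 and u = m = 10%, so the target is 1,500 cases.

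- Recorded-village share: 1,215 + 135 + 135 = 1,485, which is 15 short (1.0%).
- All-confirmed share: correction 2 falls to 135 × 0.9 = 121.5 and the total to 1,471.5, which is 28.5 short (1.9%).
- With the third term (10,000 × 0.1 × 0.1 × 0.3 × 0.5 = 15) and the recorded-village share, the total is exactly 1,500.

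**If the two kinds of missingness are correlated.** On the recorded-village reading, the undercount is the proportion missing both items. At 10%/10% with an assumed correlation of 0.3, that is 0.01 + 0.3 × 0.09 = 3.7%, not 1%.

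**Effect on the incidence rate ratio (IRR).** With equal rates in both arms the factor cancels, and the design value of 0.74 stays 0.74. As a deliberately uneven illustration, let both rates be 5% in one arm and 20% in the other.

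- Recorded-village share: 0.74 × 0.96/0.9975 = 0.712, or 0.74 × 0.9975/0.96 = 0.769 with the arms reversed.
- All-confirmed share: 0.690 or 0.794.

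**The case against.** The strongest reply is that this is a second-order gap. It is the product of two missing rates, and the documents describe steps to keep both low. Sites were chosen for a functional laboratory and regular reporting (Protocol 4.2). They receive buffer supplies and supervision (Protocol 6.1) and maps to improve residence recording (Protocol 1.5). Their data are checked monthly and queried (Protocol 12.1, SAP 5.2). This stands as an argument about size. It does not put the omitted patients into either term.

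A reader might infer that SAP 9.4 puts cases without a village into the denominator of the residence share. The text does not say so. A patient without a village cannot be classified by residence, so the share among known residences is a natural reading. SAP section 7 bases percentages on non-missing observations; that rule covers descriptive summaries and does not settle the point, but it leans the same way. The 1.9% and 7.2% figures are therefore conditional on the less favourable reading.

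A reader might also infer a biased treatment effect or a material loss of power. The documents give no reason to expect missingness to differ by arm, and Protocol 4.2 sought MRCs with a comparable level of care within each district. Between-cluster noise is also minor. Even on the all-confirmed reading, with u = m spread evenly over 0–30% across clusters and unrelated to incidence (an assumption), the recovered fraction has a relative standard deviation of about 4.9%. The design coefficient of variation moves from 0.42 to about √(0.42² + 0.049²) = 0.423.

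Finally, the downward direction depends on village being missing at random. If patients from further away more often lack a village entry, the recorded-village share overstates target-area residence and the correction could overshoot. That caveat stands, and correction 2 already carries it.

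**Conclusion.** The gap is real and small. As written, SAP 9.4 omits suspected, untested patients without a village. Under the missing-at-random assumptions above, target-area cases are undercounted by at least the proportion of suspected patients missing both items. The unstated denominator is an ambiguity rather than a demonstrated error.

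The effect falls mainly on absolute incidence. The documents do not support a claim that the primary IRR is biased, since that would require missingness to differ by arm. Nor do they establish that the cost-effectiveness ratios are understated. Protocol 10.3 and SAP 8.3 define the effectiveness measure from confirmed cases over population without mentioning the corrections, and SAP 8.3 defers the analyses to the Health Economics Analysis Plan. Cases averted would be lowered only if that plan uses the corrected counts.

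**What to change.** In SAP 9.4:

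1. Add a third term: suspected, untested patients with village missing × test positivity rate × target-area share. Residence is unknown for these patients, so the positivity that pairs with a share taken among confirmed cases is the rate among all tested suspected patients at that MRC. The worked example uses a single positivity, so this choice makes no difference there.
2. State that the share, in this term and in correction 2, is confirmed cases residing in the target area divided by confirmed cases with a recorded village.
3. Report by arm the proportions untested and without a village, and the number missing both. This shows directly whether the IRR could be touched.

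The cost is a few sentences in the SAP, a small change to the code and a short table. All the fields are already in the outpatient register. The downside is continued reliance on village being missing at random with respect to residence. The register also records parish, which could be used to check that assumption where village is blank.
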